**Reference therapy, dosage and mode of administration:**

Not applicable.

**Criteria for evaluation:**Safety Endpoints

- Incidence, type, and severity of AEs and serious adverse events (SAEs) associated with Cannabidiol Oral Solution (i.e., treatment-emergent adverse events [TEAEs]).
- Changes from baseline in vital signs, ECG findings, and laboratory values (hematology, chemistry, and urinalysis).
- Changes from baseline in neurological exam.

Baseline is defined as Visit 6 of INS011-17-103.

**Statistical Methods:**Safety Analysis

All safety assessments, including AEs, clinical laboratory evaluations, vital signs, 12-lead ECGs, physical examination (including height and weight), and neurological examinations will be listed for each visit. When appropriate, they will be summarized with descriptive statistics by age and dose cohort. The Medical Dictionary for Regulatory Activities (MedDRA; Version 20.0 or higher) will be used to classify all adverse events with respect to system organ class and preferred term. Adverse event summaries will include only TEAEs, which will be summarized for each treatment group.

- Clinical laboratory findings and vital signs will be summarized for all patients for observed values and change from baseline. Shifts from baseline to outside normal range criteria will also be presented for all patients.
- The neurological examination results will be listed and summarized descriptively. Shifts from baseline according to normal and abnormal criteria will also be presented for all patients.
- Results of physical examinations conducted throughout the study will be presented in listings and summarized descriptively. Shifts from baseline according to normal and abnormal criteria will also be presented for all patients.
- Concomitant medications and AEDs will be reported in the data listings.
- Statistical analyses will be performed using SAS® (Version 9.3 or higher, SAS Institute Inc.) or R (Version 3.3 or higher, Roswell Park Cancer Institute).

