### 3. INVESTIGATIONAL PLAN

#### 3.1. Overall Study Design

This is a multicenter, open-label, flexible dose study designed to assess the long-term safety and tolerability of CBD in doses ranging from 20 mg/kg/day to 40 mg/kg/day in patients with treatment-resistant childhood absence seizures. Patients must have completed INS011-17-103 to be eligible.

The Investigator will ensure that the patients legal representative [parent(s)/caregiver(s)] will receive a copy of the informed consent form for review and provide full informed consent prior to study participation.

Patients should enroll in Long-Term Safety Study (INS011-17-113) after completing Study INS011-17-103 Visit 6 (End of Study) to avoid interruption of the investigational product. Patients will have up to 2 weeks to enroll in INS011-17-113. The first visit (Visit 1) for INS011-17-113 will be after the completion of Visit 6 of INS011-17-103.

Patients will continue to receive CBD treatment for approximately 48 weeks. Patients will remain on their assigned dose or may be titrated up to a higher dose level if the Data Monitoring Committee has approved the higher dose level in INS011-17-103. **If any participant does not enroll within the 2 week window, the patient will not be eligible to enroll into the study.**

The study will consist of a Safety Period (48±2 weeks), Taper Period (10±3 days), and a Follow-up Period (30±5 days). Treatment visits will be scheduled monthly for the first 3 months and then quarterly over the remaining 9 months. All patients will complete a Visit 7 (End of Study) or Early Withdrawal Visit regardless of when they stop treatment/complete the study. A Follow-Up telephone call (Visit 9) will occur 30 days after the end of either the End of Study (Visit 7) or Early Withdrawal.

In this study, all patients will be dosed as follows:

- Once the informed consent for INS011-17-113 is provided within the required time frame, initially the patient will receive the same dose as was administered during INS011-17-103. If tolerability issues occurred during INS011-17-103, the dose can be decreased if the dose was greater than 20 mg/kg/day. If the patient received 20 mg/kg/day and the physician wants to decrease the dose, the patient should be discontinued.

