#### **6.1.8. Adverse Events and Serious Adverse Events**

##### **6.1.8.1. Definition of Adverse Events**

An AE is defined as any untoward medical occurrence in a patient administered a pharmaceutical product during the course of a clinical investigation. An AE can therefore be any unfavorable and unintended sign, symptom, or disease temporally associated with the use of an investigational product, whether or not thought to be related to the investigational product.

Patients will be monitored throughout the study for AEs. Monitoring for treatment-emergent AEs will begin as soon as the patient is dosed. All AEs must be followed until they are resolved or stabilized, or until all attempts to determine resolution of the event are exhausted. The investigator should use their discretion in ordering additional tests as necessary to monitor the progress of such events.

An AE may be:

- A new illness, not documented in the patient's medical history;
- Worsening of a concomitant illness;
- An effect of the study medication; it could be an abnormal laboratory value, as well as a significant shift from baseline within normal range which the qualified investigator or medical qualified designate considers to be clinically important;
- A combination of two or more of these factors.

Surgical procedures themselves are not AEs. They are therapeutic measures for conditions that required surgery. The condition for which the surgery is required is an AE, if it occurs or is detected during the study period. Planned surgical measures permitted by the clinical study protocol and the conditions(s) leading to these measures are not AEs, if the condition(s) was

(were) known before the start of study treatment. In the latter case, the condition should be reported as medical history.

Absence seizures will not be considered AEs. However, new seizure types and injury resulting from a seizure will be captured as AEs.

Patients will be monitored throughout the study for AEs. All AEs must be followed until they are resolved or stabilized, or until all attempts to determine resolution of the event are exhausted. The investigator should use his/her discretion in ordering additional tests as necessary to monitor the progress of such events.

Adverse events reported prior to dose administration will be recorded as part of the patient's medical history.

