Previous clinical trial experience has shown that somnolence, diarrhea, and transaminase elevations may be associated with CBD treatment. Therefore, Insy Development Company has identified these as Adverse Events of Special Interest.

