## 8. STATISTICS

### 8.1. Safety Endpoints

Changes in safety endpoints will be reported as mean/median change from baseline at relevant time points and as a listing of events that fall outside normal limits. Baseline is defined as Visit 6 of INS011-17-103.

- Incidence, type, and severity of AEs and serious adverse events (SAEs) associated with Cannabidiol Oral Solution (i.e., treatment-emergent adverse events [TEAEs]).
- Changes from baseline in vital signs, physical exam (including height and weight), ECG findings, and laboratory values (hematology, chemistry, and urinalysis).
- Changes from baseline in neurological exam.

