##### **8.4.3.1. Adverse Events**

The Medical Dictionary for Regulatory Activities (MedDRA, version 20.0 or higher) will be used to classify all AEs. Adverse event summaries will include only TEAEs, which will be summarized for each modal dose group. For each patient, the modal dose is the dose with the longest exposure during the study.

The number and percentage of patients with AEs will be displayed for each treatment group by system organ class and preferred term. Summaries of AEs by severity and relationship to the IP will also be provided. Serious AEs (SAEs) and AEs resulting in discontinuation will be summarized separately in a similar manner. Patient listings of AEs and SAEs will be produced.

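### Symptom-type adverse events that began on CBD in INS011-17-103 and persist unchanged are, on the natural reading, left out of the adverse event tables of INS011-17-113

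*Combined protocol and SAP*

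**What the plan says.** Section 3.1 limits entry to rollover patients: "Patients must have completed INS011-17-103 to be eligible". They start on their 103 dose, which may be lowered after tolerability problems if it was above 20 mg/kg/day. On timing, the section says: "Patients will have up to 2 weeks to enroll in INS011-17-113".

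Section 6.1.8.1 sets the AE clock with two sentences: "Monitoring for treatment-emergent AEs will begin as soon as the patient is dosed" and "Adverse events reported prior to dose administration will be recorded as part of the patient's medical history". Neither names the study whose dose is meant. Section 6.1.8.4 captures serious events from consent; no equivalent is given for non-serious events.

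Section 8.4.3.1 restricts the tables: "Adverse event summaries will include only TEAEs, which will be summarized for each modal dose group". The Synopsis has the same restriction by treatment group: "Adverse event summaries will include only TEAEs, which will be summarized for each treatment group". Section 8.1 fixes an on-treatment reference: "Baseline is defined as Visit 6 of INS011-17-103".

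The events of special interest are named in Section 6.1.8.1: "Previous clinical trial experience has shown that somnolence, diarrhea, and transaminase elevations may be associated with CBD treatment".

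**The concern.** An AE clock that starts at first dose and sends earlier events to medical history suits patients new to a drug. Here the period before the first dose of this study is itself a period of CBD treatment, so medical history can contain drug effects.

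The only objective (Section 2) is long-term safety and tolerability. Whether an early effect such as somnolence resolves or lasts through 48 weeks is part of that question. If such an event is history at entry and never changes, the AE tables cannot answer it. The loss runs in one direction: a continuing effect adds nothing to the count. The plan also expects such patients. Section 3.1 provides for entrants who had tolerability problems in 103, and exclusion 3 in Section 3.2.2 removes a patient with a related event only if the investigator judges that continuing is not in the patient's best interest.

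**Working it through.** The plan states no figure for this point. Section 8.2 gives only a cap of 30 patients, so there is nothing to reproduce. The check is of the text, followed by an illustration of size.

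**Step 1. Five cases under the two possible anchors.**

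| Case | Anchor = first 113 dose | Anchor = first 103 dose |
|---|---|---|
| Somnolence from 103, unchanged in 113 | Medical history; not in the AE tables | Treatment-emergent, but no instruction to enter it on the 113 AE page |
| Same event, worsens in 113 | New AE; counted | Counted |
| Non-serious event between Visit 6 and first 113 dose | Medical history; not in the AE tables | Treatment-emergent; entry on the 113 page not stated |
| Serious event in that gap, after consent | Captured under Section 6.1.8.4 | Captured |
| ALT elevation from 103, unchanged in 113 | Not in the AE tables; no change or shift from Visit 6; still in observed values and out-of-range listings | As for somnolence; laboratory summaries the same |

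The first column is the natural reading, because the sentences stand in this protocol without reference to another study. Under either column, nothing in the document carries an ongoing 103 event forward or plans a summary of events ongoing at entry.

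**Step 2. What remains visible.** Medical history is listed and summarised (Section 8.4.1.3), but as a baseline characteristic, with no planned causality, outcome or modal-dose breakdown.

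**Step 3. Size per patient.** 1/30 = 3.3 percentage points for a given AE term. Because 30 is a maximum and modal-dose groups are smaller, the share per patient can only be larger elsewhere.

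**Step 4. Illustration over a range.** Let N = 30, q = share entering with the event and keeping it unchanged, and p = new-onset rate in the rest.
- Share tabulated as TEAE = (1 − q)p
- Share with the event during the study = q + (1 − q)p
- Chance of at least one untabulated patient = 1 − (1 − q)^30

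The documents give no q, so it is assumed. For p, take 4/52 = 7.7%, the drug-related somnolence count in the earlier extension, INS011-14-030 (Section 1.3). This too is an assumption: the document does not say how that study treated carried-over events.

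| q (assumed) | Tabulated | Had the event on study | At least one untabulated |
|---|---|---|---|
| 5% | 0.95 × 7.7% = 7.3% | 12.3% | 0.79 |
| 10% | 0.90 × 7.7% = 6.9% | 16.9% | 0.96 |
| 20% | 0.80 × 7.7% = 6.2% | 26.2% | above 0.99 |
| 30% | 0.70 × 7.7% = 5.4% | 35.4% | above 0.99 |

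With p = 20%, the pairs are 19.0% against 24.0% at q = 5% and 14.0% against 44.0% at q = 30%. The gap between the two columns always equals q. The tabulated share falls as q rises, because patients who already have the event cannot newly develop it.

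**The case against.** The strongest case against is that the plan does not clearly exclude these events. The AE definition in Section 6.1.8.1 has a separate limb for effects of the study drug, with no requirement that they be new or worse, and an investigator could record persisting somnolence under it. TEAE is never defined by onset, and Section 8.1 glosses it as events associated with the product. Section 8.4 leaves analysis detail to a SAP to be finalised before database lock, and the 103 protocol may govern follow-up of its own ongoing events. These points stand in part. A reader might infer that only a worsening could ever count; the drug-effect limb means the text does not establish that. But the medical-history sentence is the specific instruction for events reported before dosing. If sites can read the two provisions differently, recording will vary between them, which also needs correcting.

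A second objection is that other summaries show persistent effects, and for laboratory values this is right. Section 8.4.3.2 summarises observed values at every visit and Section 8.1 lists values outside normal limits, so a lasting transaminase elevation is not hidden. The brief neurological examination covers mental status, coordination and gait at each clinic visit, and withdrawal reasons are tabulated. None of these reports diarrhea or somnolence as an event with severity and causality.

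Third, the endpoint is incidence, and a table of new events does not misstate incidence. That also stands: the missing quantity is on-study prevalence.

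Finally, entry criteria and the option to lower the dose reduce the number carrying an event, two weeks is an upper limit on the enrolment window, and the plan aims to avoid interrupting treatment. These points limit the size but do not remove the gap.

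**Conclusion.** The point holds for the AE tables and for symptom-type events. On the natural reading of the anchor, an event such as somnolence or diarrhea that began on CBD in 103 and persists unchanged is counted zero times in the 113 TEAE tables. Non-serious events in the interval before the first 113 dose are treated likewise. If the 103 dose was meant, the plan must say so and still needs a carry-forward rule.

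A reader might infer that persistent CBD effects vanish from the whole safety report, or that a given percentage is lost. The documents support neither. Laboratory effects remain visible in observed values and listings, though they cancel in change and shift summaries against the Visit 6 baseline. The number of affected patients is unknown; only the 3.3 points per patient at N = 30 follows from the plan, and the tables above rest on assumed values of q and p. For a study whose sole objective is long-term safety and tolerability, the correction should be made, and it is cheap.

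**What to change.** In Section 6.1.8.1, name the dose and study that anchor treatment emergence. For rollover patients, replace the medical-history sentence: any AE ongoing at Visit 6 of 103, or starting between Visit 6 and the first 113 dose, goes on the 113 AE page with its original onset date, severity and causality and a carry-over flag. The flag prevents double counting in any pooled 103/113 analysis. Reserve medical history for conditions that predate the first CBD dose in 103.

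In Section 8.4.3.1, keep the table of new or worsened TEAEs as the incidence summary. Add one table of AEs ongoing at entry, by system organ class and preferred term with the events of special interest flagged, showing how many resolved, persisted or worsened, together with on-study prevalence (ongoing plus new).

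The cost is protocol wording, modest extra data entry and one table, with no new visits or procedures. Reported AE frequencies will look less favourable than under the TEAE table alone.

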#### 6.1.8.2. Classification of Adverse Events

Adverse events are to be recorded on the AE page of the patient's case report form (CRF). Severity will be graded according to the following definitions:

- **Mild:** The patient experiences awareness of symptoms but these are easily tolerated or managed without specific treatment.
- **Moderate:** The patient experiences discomfort enough to cause interference with usual activity, and/or the condition requires specific treatment.
- **Severe:** The patient is incapacitated with inability to work or do usual activity, and/or the event requires significant treatment measures.

Action taken will be categorized as none, study drug discontinued, dose modified, required concomitant medication, required procedure, or other.

Event outcome at resolution or time of last follow-up will recorded as event resolved, resolved with sequelae, ongoing, or death.

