### 3.5. Stopping Rules

The investigator reserves the right to terminate the study in the interests of patient safety and welfare. The Sponsor reserves the right to terminate the study at any time for administrative reasons.

Patients will also be discontinued from the study if they meet the following criteria:

- ALT or AST  $> 3 \times$  ULN with (or the appearance of) fatigue, nausea, vomiting, right upper quadrant pain or tenderness, fever, rash, and/or eosinophilia  $> 5\%$
- ALT or AST  $> 8 \times$  ULN
- ALT or AST  $> 5 \times$  ULN for more than 2 weeks
- ALT or AST  $> 3 \times$  ULN and bilirubin  $> 2 \times$  ULN or INR  $> 1.5$

For patients meeting the above criteria, the investigator will arrange for the patient to return to the investigational site as soon as possible (within 24 hours of notice of abnormal results) for repeat assessment of ALT, AST, bilirubin, and alkaline phosphatase (ALP), detailed history, and physical examination. Patients will be followed until all abnormalities have normalized (in the investigator's opinion) or returned to the baseline state. If the patient is unable to return to the investigational site, repeat assessments may be performed at a local laboratory.

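### The only AE severity scale has no criterion for symptom-free laboratory events, so a transaminase rise at discontinuation level has no defined grade unless treatment is required

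*Combined protocol and SAP*

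**What the plan says.** Section 6.1.8.2 defines three grades.

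- The lowest grade (Mild) presupposes that symptoms are noticed: "The patient experiences awareness of symptoms but these are easily tolerated or managed without specific treatment".
- The middle grade (Moderate) can be reached by a symptom route or a treatment route: "The patient experiences discomfort enough to cause interference with usual activity, and/or the condition requires specific treatment".
- The top grade (Severe) offers the same two routes at a higher level: "The patient is incapacitated with inability to work or do usual activity, and/or the event requires significant treatment measures".

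No other severity scale appears, and 6.1.8.7 sends the investigator back to this one for rating intensity.

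Section 6.1.8.1 allows an AE to be a laboratory finding ("it could be an abnormal laboratory value"). It also records earlier experience that "somnolence, diarrhea, and transaminase elevations may be associated with CBD treatment", and makes these three the AEs of special interest.

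Section 3.5 introduces its hepatic criteria with "Patients will also be discontinued from the study if they meet the following criteria". They are:

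- ALT or AST above 3 x ULN with listed symptoms or signs and/or eosinophilia above 5%;
- above 8 x ULN;
- above 5 x ULN for more than 2 weeks;
- above 3 x ULN with bilirubin above 2 x ULN or INR above 1.5.

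Severity is part of the first endpoint in 8.1 ("Incidence, type, and severity of AEs and serious adverse events (SAEs) associated with Cannabidiol Oral Solution") and is tabulated under 8.4.3.1 ("Summaries of AEs by severity and relationship to the IP will also be provided").

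**The concern.** The protocol expects AEs that are purely laboratory findings and singles one of them out for special attention, but its severity scale does not describe them. A raised transaminase is often noticed only on the laboratory report. If the child feels well and nothing is prescribed, the investigator has no stated basis for choosing a grade, whether the value is just above normal or high enough to end participation.

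What is at stake is the meaning of the severity table for the hepatic AE of special interest. A reader of the study report would expect that table to show how serious the transaminase events were. As the scale stands, the grade would reflect each investigator's own convention, and two sites could grade the same value differently.

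**Working it through.** No arithmetic applies: the plan states no figure on this point and gives no event rate. The check sets the definitions against the cases the protocol itself foresees.

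**Step 1. Can the discontinuation criteria be met without symptoms?** Yes, all four. Three are stated in laboratory terms, plus duration in one of them. The remaining one joins eosinophilia to the symptom list by and/or, so it can also be read as met on laboratory values alone.

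**Step 2. Does stopping study drug count as treatment?** The protocol does not say so, and its layout points the other way. In 6.1.8.2, discontinuation of study drug is one category of action taken, separate from concomitant medication and from a procedure, and no category is tied to a grade. In 6.1.8.5, the SAE actions likewise list treatment and drug withdrawal as different items.

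**Step 3. Apply the three definitions literally to a transaminase AE.**

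| Case | Mild | Moderate | Severe |
|---|---|---|---|
| Feels well, no treatment, drug stopped only | Not met: no symptoms | Not met | Not met |
| Feels well, specific treatment required | Not met | Met by the treatment clause | Not met |
| Feels well, significant treatment measures required | Not met | Superseded | Met by the treatment clause |
| Symptoms that interfere with activity | Not met | Met | Met if incapacitated |

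The first row is the gap. It holds equally for an illustrative ALT of 1.2 x ULN recorded as an AE and for one of 9 x ULN that triggers 3.5. Nothing in the scale ranks the second above the first.

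**Step 4. Does another planned summary restore the distinction?**

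- Laboratory shifts (synopsis, Statistical Methods) are to outside the normal range. Values of 1.2 x and 9 x ULN fall in the same cell.
- Descriptive statistics by visit (8.4.3.2) may show the largest value at a visit, because 8.4 includes the maximum. They do not count patients above a multiple of ULN, and they cover the scheduled visits in Table 1.
- The listing of values outside normal limits (8.1) holds the individual values, but it is not a summary.
- Section 8.4.3.1 summarizes discontinuation AEs and SAEs separately. It plans no summary specific to the AEs of special interest.

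Magnitude can therefore be recovered patient by patient from listings, but not from any planned summary table.

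**The case against.** The strongest case on the other side has five parts.

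- **Other outputs carry the information.** AEs leading to discontinuation are summarized whatever their grade, so a child removed under 3.5 will appear there. A medically significant event can also be an SAE under 6.1.8.4. With at most 30 patients, the listings can be read in full. This stands, and it confines the problem to the severity table. It does not repair that table.
- **Section 3.5 is a discontinuation rule, not a severity ranking.** This also stands. The two sections do not contradict each other; the scale simply has no place for the event.
- **The gap may be closed elsewhere.** Section 8.4 promises a detailed SAP before database lock, and 9.4.1 and 9.4.2 refer to CRF completion guidelines. Either could add a grading rule. The combined document contains none, and a rule that investigators must apply at the visit belongs in the protocol.
- **The ULN multiples in 3.5 are not ready-made severity bands.** They are tied to duration, symptoms, bilirubin or INR. This stands, and is why the grading should come from a named table, with the multiples used only for a descriptive summary.
- **Anemia does not prove the same point.** Section 1.3 reports it in 5 subjects of the earlier long-term study, but does not say whether they were symptom-free or untreated. It shows only that AEs of this kind can be expected.

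A reader might infer that symptom-free laboratory AEs can only be graded Mild. The text does not say that: Mild presupposes symptoms, and the treatment clauses of Moderate and Severe can be met without them.

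**Conclusion.** The gap is real. The sole severity scale has no criterion for a symptom-free laboratory AE, so a transaminase event of special interest, even at a level that 3.5 treats as requiring discontinuation, fits no defined grade unless treatment is required.

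It would be tempting to conclude that the severity endpoint is biased downwards. The documents do not support that. An investigator may default to Mild as the nearest grade, or may grade higher because 3.5 demands removal, prompt return and follow-up. What follows from the text is an undefined grade and probable inconsistency between sites, not a known direction of error.

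No numerical size can be given, because the documents contain no rate for such events and do not say how patients will divide among the modal dose groups used in 8.4.3.1. The effect is limited to the severity summary in a descriptive study with no inferential safety analysis. The conclusion rests on one reading: that stopping study drug is an action taken and not a treatment. Sections 6.1.8.2 and 6.1.8.5 support this but do not define it. The change is worth making because it concerns a named AE of special interest and an endpoint component, and it costs little.

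**What to change.** - **Section 6.1.8.2.** State that an AE which is a laboratory abnormality is graded from the measured value, using one named standard laboratory grading table with its grades mapped to mild, moderate and severe. Keep the present definitions for clinical AEs. Use the resulting grade in the severity summary of 8.4.3.1.
- **Section 8.4.3.** Add a table of each patient's maximum post-baseline ALT and AST, counting patients above 3, 5 and 8 x ULN, the multiples already printed in 3.5. Include unscheduled and repeat values, since 3.5 allows repeat tests outside the visit schedule and at local laboratories.

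No stopping or dosing rule changes. The cost is a paragraph in the protocol, a CRF completion note and one extra table. ALT and AST are already collected at every scheduled clinic visit of the Safety Period and at early withdrawal. The downside is that some laboratory AEs may be reported as more severe than investigators would have graded them under the present wording.
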